2. List of Abbreviations and Definitions of Terms

Abbreviation	Definition
AF	Atrial Fibrillation
AE	Adverse Event
AV	Atrioventricular
CEC	Clinical Events Committee
CIP	Clinical Investigation Plan
CRF	Case Report Form (synonomous with eCRF)
CT	Computerized Tomography
DMC	Data Monitoring Committee
ECG	Electrocardiogram
eCRF	Electronic Case Report Form (synonomous with CRF)
eGFR	Estimated Glomerular Filtration Rate
FMD	Fibromuscular Dysplasia
LBBB	Left Bundle Branch Block
MI	Myocardial Infarction
mITT	Modified Intention-To-Treat
MR	Magnetic Resonance
MRI	Magnetic Resonance Imaging
NYHA	New York Heart Association
PCI	Percutaneous Coronary Intervention
PCTA	Percutaneous Transluminal Angioplasty
PVI	Pulmonary Vein Isolation
RF	Radio Frequency

SAP	Statistical Analysis Plan
TIA	Transient Ischemic Attack
UADE	Unanticipated Adverse Device Effect

3. Introduction

Study Purpose

The purpose of the Symplicity AF clinical study is to evaluate the feasibility of performing both renal artery denervation and pulmonary vein isolation on the same patient with the intent of characterizing both safety and effectiveness in a paroxysmal and persistent atrial fibrillation (AF) population with hypertension. To assess safety, a primary objective will measure the occurrence of a composite safety endpoint and, to assess effectiveness, a primary objective will measure freedom of chronic treatment failure through a minimum of six months of follow-up. The market released Arctic Front Advance™ Cardiac Cryoablation system and investigational Symplicity™ Renal Denervation system (Multi-Electrode Renal Denervation Catheter and the Symplicity G3™ Renal Denervation RF Generator, hereafter referred to as the Symplicity Spyral Catheter and Symplicity G3 Generator) will be used in the study. The Arctic Front Advance Cardiac Cryoablation system is not approved in the United States for the treatment of persistent AF, therefore it is considered investigational in this patient population.

This feasibility study has been designed to support the following proposed Indication for Use should Medtronic choose to study this further:

Renal denervation with the Symplicity System increases the success rate and augments the benefits of pulmonary vein isolation with the Arctic Front Advance System in patients with symptomatic drug refractory paroxysmal and persistent AF and uncontrolled hypertension for the prevention of AF recurrence.

A randomized design was selected to compare safety and effectiveness between subjects receiving both renal artery denervation and pulmonary vein isolation within one procedure (Treatment arm) and subjects receiving only pulmonary vein isolation (Control arm). The randomized design will help minimize biases and control for confounding factors between comparison groups. Subjects and center personnel will be blinded to the randomization assignment until after the pulmonary vein isolation procedure.

Statistical Analysis Plan Purpose

This Statistical Analysis Plan (SAP) documents, before data is analyzed, the planned analyses that will be included in the Symplicity AF final report. Additionally, reports and analysis created for the Data Monitoring Committee (DMC) will use this SAP for guidance. Analyses for Symplicity AF publications will not be limited to this SAP.

This plan does not limit the analysis that may be provided in reports or publications.

The Symplicity AF Clinical Investigation Plan (CIP) version 12, dated 24/JUN/2016, was used to develop the SAP. Version 16 of the CIP, dated 23/MAY/2018, was used to update the SAP, largely to reflect the inclusion of an interim analysis.

4. Study Objectives

Primary Objectives

1. Safety: The primary safety objective characterizes the rate of safety composite events within each of the two study arms and also characterizes the difference in the rates between study arms.
2. Effectiveness: The primary effectiveness objective compares the rate of chronic treatment success between study arms.

Secondary Objective

1. The secondary effectiveness objective characterizes the rate of chronic treatment success in Treatment and Control arms in the subgroup of subjects that do not undergo an additional pulmonary vein ablation procedure during the 90 day blanked follow-up period.

Ancillary Objectives

The ancillary objective endpoints below will be compared between study arms in order to further characterize the differences in outcomes between patients randomized to pulmonary vein isolation only to those randomized to pulmonary vein isolation and renal artery denervation.

1. Office systolic and diastolic blood pressure at 6 months compared to baseline
2. Heart rate at 6 months compared to baseline
3. Procedural measures (total procedure time, cryoablation procedure time, renal artery denervation procedure time, ablation time, fluoroscopy time, dye usage)
4. Symptoms at 6 months compared to baseline
5. Freedom from chronic treatment failure and off Class I and III antiarrhythmic drugs following the blanking period
6. AF burden (percent of time in AF) over all follow-up after the blanking period

5. Investigation Plan

[figure not shown]
5.1. Study Design Summary

The Symplicity AF study is a prospective, randomized, multi-center, investigational, feasibility, clinical study. The study is expected to be conducted at up to 12 centers located in The United States. Up to 245 subjects will be enrolled in the study to ensure there are 70 randomized subjects. The number of

enrollments permitted relative to the number of subjects to be randomized is high since it is expected that a fair number of subjects will not meet all screening criteria (rigorous blood pressure monitoring and renal anatomy) once consented. Center randomization will be capped at 30% (21) of the total randomized subjects.

Randomized study subjects will be followed for a minimum of six months, and then every six months thereafter until official study closure as determined by Medtronic and/or regulatory authority, whichever occurs first. Accordingly, the expected total study duration, if the study conducts a final analysis, is approximately fifty-seven months, representing approximately fifty-one months of enrollment and six months of subject follow-up after the last patient has undergone the study procedure. The figure below illustrates the study design.

Interim analyses of the primary effectiveness objective may take place and if data are deemed to sufficiently characterize this study objective by the sponsor at one of these analyses, enrollment may be stopped.

Figure 1. Study Design Flowchart

Two interim analyses are planned. The first analysis will be conducted after 32 subjects are randomized and have completed their six-month visit. If the primary effectiveness objective is not passed after this analysis, the second will be conducted after 50 patients have been randomized and have completed their six-month visit. If neither interim analysis results in a successful primary effectiveness objective, the final analysis will be conducted once 70 patients are randomized and have completed their six-month visit.

5.2. Subject Selection Criteria

Subjects will be screened to ensure they meet all of the inclusion and none of the exclusion criteria. Institutional Review Board and Medtronic approval of the Symplicity AF CIP and Informed Consent Form must be obtained prior to enrolling subjects in the study. Enrollment of the subject must occur prior to any study procedures take place.

5.2.1. Inclusion Criteria

- Drug refractory recurrent symptomatic paroxysmal or persistent atrial fibrillation
 - Drug refractory is defined as: failed (drug is ineffective, or patient is intolerant) at least one Class I or III anti-arrhythmic drug
 - If the subject has persistent atrial fibrillation it must have been diagnosed within the last two years from the date of consent with a left atrial volume index $\leq 40 \text{ ml/m}^2$ within the last year from the date of consent
- Office-based systolic blood pressure $> 140 \text{ mm Hg}$ based on average of three blood pressure readings despite treatment with 1 or more antihypertensive medication. The subject should be on a stable antihypertensive drug regimen with no changes for a minimum of 2 weeks prior to enrollment and the antihypertensive drug regimen is not expected to change for at least 6 months, as determined by the subject's referring cardiologist and/or the investigator.
- Age 18 years to 80 years old
- Willing to give informed consent and agree to all study procedures, and is competent and willing to provide written, informed consent to participate in this clinical study
- Willing and able to be remotely monitored through the Medtronic CareLink® Network

5.2.2. Exclusion Criteria

- Active systemic infection
- Cryoglobulinemia
- One or more pulmonary vein stents

- Type I Diabetes
- NYHA Class IV heart failure with in the past 6 months
- Renal artery anatomy that is ineligible for treatment including:
 - Lacks at least one renal artery for each kidney with ≥ 3 mm and ≤ 8 mm diameter and minimum treatable length per the Spyral Instructions for Use prior to a significant arterial branch (*NOTE: All renal arteries with ≥ 3 mm and ≤ 8 mm diameter with minimum treatable length per the Spyral Instructions for Use shall be treated, including dual renal arteries meeting these morphologic criteria.*)
 - Renal artery stenosis ($>50\%$) or renal artery aneurysm in either renal artery
 - A history of prior renal artery intervention including balloon angioplasty or stenting
 - Renal artery which contain calcification which does not allow at least four radio frequency ablations to be delivered
 - Diffuse fibromuscular dysplasia (FMD) or FMD which does not allow at least four radio frequency ablations to be delivered; FMD defined as visible beading of the artery on angiography
 - Unilateral kidney
- Estimated Glomerular Filtration Rate (eGFR) of <30 mL/min/1.73m²
- Primary pulmonary hypertension
- Pheochromocytoma, Cushing's Disease, coarctation of the aorta, untreated hyperthyroidism, primary hyperparathyroidism or hyperaldosteronism (Note: treated hyperthyroidism is permissible)
- Myocardial infarction, unstable angina pectoris, syncope, PCI/PTCA, or coronary artery stenting within 3 months prior to signing the consent form, or has widespread atherosclerosis with documented intravascular thrombosis or unstable plaques
- Cerebrovascular accident or TIA within 1 month prior to signing the consent form
- Prior ablation for atrial fibrillation in the left atrium
- Presence of a permanent pacemaker, biventricular pacemaker, atrial defibrillator or any type of implantable cardiac defibrillator (with or without biventricular pacing function)
- Cardiac valve stenosis for which a significant reduction of blood pressure is contraindicated
- A condition that would prohibit or interfere with ability to obtain an accurate blood

pressure measurement using the protocol-specified automatic blood pressure monitor (e.g., arm diameter too large for the cuff)

- Serious medical condition, which may adversely affect the safety and/or effectiveness of the participant or the trial (e.g., patients with clinically significant peripheral vascular disease, abdominal aortic aneurysm, bleeding disorders such as thrombocytopenia, hemophilia, or significant anemia)
- Pregnant, nursing or planning to be pregnant. [Female participants of childbearing potential must have a negative serum or urine human chorionic gonadotropin (hCG) pregnancy test prior to angiography]
- Known history of drug use or alcohol dependency, lacks the ability to comprehend or follow instructions, or would be unlikely or unable to comply with study follow-up requirements
- Previous organ transplant
- Currently enrolled or plans to participate in a potentially confounding drug or device trial during the course of this study. Co-enrollment in concurrent studies is allowed when documented pre-approval is obtained from the Medtronic study manager.

5.3. Randomization and Blinding

Randomization schedules will be prepared for each site using a random permuted block design stratified by center and AF diagnosis. The schedules will allocate subjects in a 1:1 ratio to the treatment or control arm. Each center will receive a set of sequentially numbered envelopes labeled specifically for that center that is labeled with one randomization code per envelope. After a CT scan has been performed and confirmed that the renal anatomy meets eligibility requirements, the subject will be randomized. The next sequential envelope labeled with a randomization code will be used. The envelope number will be recorded for each randomized subject and communicated to Medtronic. The sequence of subject randomization will be checked to ensure it matches the sequence of envelope numbers.

Randomization assignments are the following:

- Treatment:
 - Perform the pulmonary vein isolation procedure, renal angiogram, renal artery denervation procedure and the Reveal LINQ insertion.
- Control:
 - Perform the pulmonary vein isolation procedure and the Reveal LINQ insertion. Do NOT perform renal denervation.

Enrolled subjects who were not randomized should be exited. Subjects and center personnel will be blinded to the randomization assignment until after the pulmonary vein isolation procedure. Randomization envelopes may be returned to the randomization pool if the patient is exited before revealing the randomization assignment to center personnel. Crossing over to the Treatment group once assigned to the Control group is not allowed at any point during the study.

Medtronic statisticians are planning to conduct the analyses for this study. Analyses using actual randomization assignments will not be performed until after the final database freeze except for interim analyses or analyses performed for the DMC. Unblinding for the DMC will be considered planned unblinding. The freeze intended for the final report will also be considered a planned unblinding.

Analyses of the study objectives for review by the DMC will be performed by a Medtronic statistician other than the lead statistician for the study. The lead study statistician will be blinded to all DMC analyses of study objectives. The unblinded statisticians will keep results strictly confidential per the DMC charter during the study.

The Clinical Event Committee (CEC) members may be blinded to the subjects' randomization assignment and/or other data or procedures that may influence their decision.

More details can be found in the Symplicity AF Randomization and Blinding Plan document.

5.4. Interim Analyses

Two interim analyses are planned for the study. These analyses would be performed after 32 and 50 subjects have been randomized and completed their 6-month follow-up visits, respectively. Both the sponsor and the DMC will assess the results of the interim analyses of the primary effectiveness objective and based on this assessment, the sponsor may decide to stop enrollment.

The DMC will be responsible for assessing the accumulating data on safety of the procedures during the study. The primary responsibility of the DMC is to safeguard the interests of study participants. The DMC also monitors the overall conduct of the clinical study.

5.5. Endpoint Adjudication

An independent CEC will conduct a medical review of, at a minimum, all deaths and adverse events (AE). The CEC's adjudication will be used for data analysis.

5.6. Data Monitoring Committee

A DMC will periodically review accumulating safety data for the study, including the rate of safety composite events within each study arm and the difference in the rate between study arms (i.e., the Primary Safety Objective).

6. Determination of Sample Size

The overall study sample size is 70 randomized subjects that undergo a pulmonary vein isolation procedure which is the required sample size for the primary effectiveness objective.

Subjects that are enrolled in the study may not go on to be randomized due to a variety of reasons, including elective withdrawal prior to randomization, blood pressure measurements that do not meet study criteria, or renal anatomy that is found to be ineligible upon angiography. Based on the rate of randomization among enrolled subjects in trials with similar screening criteria, up to 245 subjects may need to be enrolled and undergo screening in order to ensure that 70 subjects are randomized.

There will be at least 78% power to test the primary effectiveness objective provided at least 70 subjects undergo randomization and undergo a pulmonary vein isolation procedure. Table 1 below shows the expected incremental power at each analysis. The first and second look correspond to the interim analyses. The third interim look is the final analysis.

Table 1: Power at each stage of the analyses

Look	Patients w/ six month follow-up	Expected Incremental Power of Analysis
1	32	17.6%
2	50	10.1%
3	70	50.9%
Cumulative Power:		78.6%

Subjects who are randomized and meet either of the following two conditions do not count toward the 70 randomized subjects to be used in the mITT set (define below):

- Exit the study without undergoing a pulmonary vein isolation procedure
- Subjects who are randomized to the treatment group and are found not to meet inclusion/exclusion criteria during the renal denervation procedure

The sample size calculation is based on the following assumptions:

- 1:1 randomization
- Constant randomization rate over 16 months
- Last enrolled subject followed through 6 months post-procedure
- 50% chronic treatment success in the Control arm (PVI only) versus 75% in the Treatment arm (equivalent to a hazard ratio of 0.415) through 6 months post-procedure
- Constant hazard ratio over all follow-up
- Constant attrition (dropout) of 5% per 6 months

The original sample size calculation was performed in PASS 2008 using the log-rank (Lakatos) procedure. Updates to incorporate interim analyses were performed using EaST, version 6.4.1 with the survival module. Accounting for a study attrition rate of up to 5% per 6 months ensures that the study will maintain the planned power of 78% in case attrition is higher than expected (approximately 1% per 6 months).

A summary of the EaST output detailing the analyses is given on the following page.

Design: Survival Endpoint: Two-Sample Test - Parallel Design - Logrank Given Accrual Duration and Study Duration

Test Parameters	
Design ID	Des3
Design Type	Superiority
Number of Looks	3
Test Type	2-Sided
Specified α	0.05
Power	0.786
Model Parameters	
HR = λ_c/λ_e	
Under H0	1
Under H1	0.415
Ratio of % Surv. at Period #1:	1.5
Cum. % Surv. by Time =	6
Control (S_c)	50
Treatment (S_e)	75
Var (Log HR)	Null
Allocation Ratio (n_e/n_c)	1
Boundary Parameters	
Spacing of Looks	Unequal
Efficacy Boundary	Interp.
Accrual / Dropouts Parameters	
Cum % Accrued	100
Accrual Duration	16
Max Study Duration	22
Dropout	Yes

Variable Follow-Up Design: All subjects are followed until failure, drop out or end of study.

Sample sizes and events have been rounded.

Sample Size Information

	Control Arm	Treatment Arm	Total
Sample Size (n)			
Maximum	34	35	69
Expected H1	31.666	31.666	63.331
Expected H0	34.288	34.288	68.577
Events (s)			
Maximum	25	16	41
Expected H1	22.52	13.022	34.031
Expected H0	20.325	20.325	40.62
Dropouts (d)			
Maximum	2	3	5
Expected H1	1.723	2.547	4.27
Expected H0	1.985	1.985	3.97
Maximum Information (I):			10.25

Accrual and Study Duration

	Accrual Duration	Study Duration
Maximum	16	21.998
Expected H1	14.686	19.024
Expected H0	15.902	17.361

Stopping Boundaries: Look by Look

Look #	Info. Fraction (s/s_max)	Events (s)	Cumulative α Spent	Boundaries
Efficacy Z				
Upper		Lower		
1	0.341	14	0.01	2.576 -2.576
2	0.463	19	0.015	2.611 -2.611
3	1	41	0.05	2.049 -2.049

Events, Sample Size, Dropouts, Pipeline and Analysis Times: Look by Look (Under H0)

Look #	Info. Fraction (s/s_max)	Sample Size (n)	Events (s)	Dropouts (d)	Pipeline (n-s-d)	Analysis Time	Boundary Crossing Prob (Incremental)
Efficacy							
Upper		Lower					
1	0.341	39	14	2	23	8.863	0.005
2	0.463	46	19	2	25	10.639	0.003
3	1	69	41	4	24	17.481	0.017

Events, Sample Size, Dropouts, Pipeline and Analysis Times: Look by Look (Under H1)

Look #	Info. Fraction (s/s_max)	Sample Size (n)	Events (s)	Dropouts (d)	Pipeline (n-s-d)	Analysis Time	Boundary Crossing Prob (Incremental)
Efficacy							
Upper		Lower					
1	0.341	46	14	2	30	10.492	1.216E-5
2	0.463	55	19	3	33	12.575	1.846E-6
3	1	69	41	5	23	21.998	5.177E-7

Dropout Information : Prob. of Dropout

Period #	By Time	Control	Treatment
1	6	0.05	0.05
2	12	0.1	0.1
3	18	0.15	0.15
4	22	0.183	0.183

7. Statistical Methods

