## 12.8 Interim analysis

Interim analyses will be performed.

Two interim analysis of the primary effectiveness objective may be performed after 32 and 50 subjects have been randomized and completed their 6-month follow-up visits, respectively. Both the sponsor and the DMC will assess the results of the interim analyses of the primary effectiveness objective and based on this assessment, the sponsor may decide to stop enrollment.

Time Point of Interim Analyses of the Primary Effectiveness Objective	Cumulative Alpha	Boundary*	Pass/Fail Primary Effectiveness Objective
After 32 subjects were randomized and completed their 6-month visit	0.01	0.01	If a two-sided p-value $\leq 0.01$ , in favor of the treatment group, then the study passed the primary effectiveness objective
After 50 subjects were randomized and completed their 6-month visit	0.015	0.008	If a two-sided p-value $\leq 0.008$ , in favor of the treatment group, then the study passed the primary effectiveness objective
Final Analysis: After 70 subjects were randomized and completed their 6-month visit	0.05	0.04	If a two-sided p-value $\leq 0.04$ , in favor of the treatment group, then the study passed the primary effectiveness objective

\*Boundaries were calculated using EAST 6.4.1

In addition to reviewing the effectiveness data from the interim analyses, the DMC will be responsible for assessing the accumulating data on safety of the procedures during the study. The primary responsibility of the DMC is to safeguard the interests of study participants. The DMC also monitors the overall conduct of the clinical study. Further information regarding the DMC is found in Appendix C: Data Monitoring Committee.

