7.8. Interim Analyses

Two interim analyses are planned for the study. These analyses would be performed after 32 and 50 subjects have been randomized and completed their 6-month follow-up visits, respectively. Both the

sponsor and the DMC will assess the results of the interim analyses of the primary effectiveness objective and based on this assessment, the sponsor may decide to stop enrollment. However, while there are formally defined stopping rules for a successful primary effectiveness endpoint, there are no stopping rules for futility.

Patients randomized to the trial who have not reached 6-months of follow-up are not considered in assessing the primary effectiveness objective.

The time points of the analyses and criteria for study success are given in Table 1 below:

Table 2: Timing and Success Criteria for Interim and Final analyses

Time Point of Interim Analyses of the Primary Effectiveness Objective	Cumulative Alpha	Boundary*	Pass/Fail Primary Effectiveness Objective
After 32 subjects were randomized and completed their 6-month visit	0.01	0.01	If a two-sided p-value ≤ 0.01 , in favor of the treatment group, then the study passed the primary effectiveness objective
After 50 subjects were randomized and completed their 6-month visit	0.015	0.008	If a two-sided p-value ≤ 0.008 , in favor of the treatment group, then the study passed the primary effectiveness objective
Final Analysis: After 70 subjects were randomized and completed their 6-month visit	0.05	0.04	If a two-sided p-value ≤ 0.04 , in favor of the treatment group, then the study passed the primary effectiveness objective

*Boundaries were calculated using EaST 6.4.1, using the Survival Module.

In addition to reviewing the effectiveness data from the interim analyses, the DMC will be responsible for assessing the accumulating data on safety of the procedures during the study. The primary responsibility of the DMC is to safeguard the interests of study participants. The DMC also monitors the overall conduct of the clinical study. Further information regarding the DMC is found in Appendix C: Data Monitoring Committee.

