7.10.2.4. Analysis Methods

A log-rank test will be used to perform this hypothesis test. The log-rank test uses the time that each subject is free from chronic treatment failure, defined from the date of procedure to the date of chronic treatment failure, if it occurs, or latest of the following: a) the last follow-up visit date, or b) the last date on which AF was assessed, if chronic treatment failure does not occur during the subject's study follow-up. Subjects will be included through all available study follow-up.

In addition to the log-rank test, Kaplan-Meier curves will be used to estimate the rate of chronic treatment success. Cox proportional hazards regression will be used to estimate the hazard ratio and its 95% confidence interval between study arms.

Code similar to the following can be used for the log-rank test and Kaplan-Meier curves:

```
ODS graphics on ;
PROC LIFETEST DATA=survData conftype=loglog;
    Plots = (survival(atrisk = 0 to <end time> by <interval time>)) ;
    STRATA trtGroup;
    TIME time*event(0);
    TEST trtGroup;
RUN;
ODS graphics off ;
```

Code similar to the following can be used for the Cox proportional hazards model:

```
PROC PHREG DATA = survData;
    CLASS trtGroup;
    MODEL time*event(0) = trtGroup / TIES = efron;
RUN;
```

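### SAP Table 1 labels the powers of event-based looks (14 and 19 events) as powers at 32 and 50 six-month completers, and the printed look-2 boundary does not match the 0.008 limit

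*SAP*

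**What the plan says.** SAP section 6 introduces the stage powers with the sentence "Table 1 below shows the expected incremental power at each analysis". Table 1 indexes its rows by patients with six months of follow-up: 32, 50 and 70, with incremental powers of 17.6%, 10.1% and 50.9% (cumulative 78.6%). The assumptions beside it include "Constant randomization rate over 16 months", 50% versus 75% success at six months (hazard ratio 0.415) and 5% dropout per six months.

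The EaST summary that follows indexes its looks by events: 14, 19 and 41, with Z boundaries of 2.576, 2.611 and 2.049 for cumulative alpha of 0.01, 0.015 and 0.05. Under the alternative it places these looks at months 10.492, 12.575 and 21.998, with 46, 55 and 69 subjects accrued. It describes the design as "Variable Follow-Up Design: All subjects are followed until failure, drop out or end of study".

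SAP 7.8 sets the interim looks at 32 and 50 six-month completers and restricts who counts: "Patients randomized to the trial who have not reached 6-months of follow-up are not considered in assessing the primary effectiveness objective". SAP 7.10.2.4 adds: "Subjects will be included through all available study follow-up". For look 2, SAP Table 2 requires "If a two-sided p-value ≤ 0.008 , in favor of the treatment group", and the protocol's table in 12.8 gives the same 0.008. The protocol says "Boundaries were calculated using EAST 6.4.1", and SAP Table 2 carries a matching footnote.

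**The concern.** Table 1 is the SAP's only statement of how likely the study is to pass at each look, and after an interim look "the sponsor may decide to stop enrollment". If the percentages were computed for looks at other times, with other event counts and another set of subjects, the reader is misinformed about the chance of early success.

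The SAP also carries two look-2 boundaries from the same software. A p-value between 0.008 and 0.009 would fail Table 2 but cross the boundary in the printout.

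**Working it through.** **Inputs.** All come from SAP section 6 unless noted: control hazard ln 2/6 per month; treatment hazard −ln 0.75/6; dropout hazard −ln 0.95/6; HR = ln 0.75/ln 0.5 = 0.415; uniform accrual over 16 months; N = 69 in the EaST run and 70 planned. Hazards are constant from day 0. For a log-rank test with 1:1 allocation and d events, the mean of Z is √d × |ln HR|/2 = 0.4397√d.

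**1. Reproduce Table 1.** At look 1, √14 × 0.4397 = 1.645, and 1 − Φ(2.576 − 1.645) = 17.6%. Carrying the three looks through by numerical integration at 14/19/41 events with Z = 2.576/2.611/2.049 gives increments of 17.6%, 10.1% and 50.9%, total 78.6%. This is an exact match. The opposite-tail increments come out at 1.215E-5, 1.850E-6 and 5.165E-7, against the printed 1.216E-5, 1.846E-6 and 5.177E-7. Table 1 therefore gives the powers of the event-based looks.

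**2. Confirm the model.** For an arm with hazard λ, dropout η and accrual rate r, expected events by month t are r·λ/(λ+η) × ∫[1 − e^−(λ+η)(t−u)]du over entry times u. At months 10.492, 12.575 and 21.998 with N = 69 this returns 14.0, 19.0 and 41.0.

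**3. Count subjects at six months at those times.**
- Look 1: (10.492 − 6) × 69/16 = 19.4, not 32.
- Look 2: (12.575 − 6) × 69/16 = 28.4, not 50.
- Final: about 69, so row 3 is correctly labelled.

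With N = 70, 32 subjects reach six months at 32/70 × 16 + 6 = month 13.3, and 50 at 50/70 × 16 + 6 = month 17.4. Both EaST interim looks precede the first planned look.

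**4. Power at the planned looks**, using the Table 2 limits 0.01/0.008/0.04. Completers here are subjects randomised at least six months before the look.

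| Reading | Expected events | Cumulative power, analytic | Cumulative power, simulated | Cumulative alpha |
|---|---|---|---|---|
| Completers, 16-month accrual | 15.9 / 27.4 / 41.6 | 20.5 / 39.9 / 79.0% | 18.6 / 37.6 / 77.7% | 0.0100 / 0.0155 / 0.0480 |
| All accrued, 16-month accrual | 21.2 / 32.4 / 41.6 | 29.1 / 47.7 / 79.0% | 25.9 / 44.1 / 76.1% | 0.0100 / 0.0149 / 0.0458 |
| Completers, 51-month accrual (SAP 5.1) | 20.8 / 35.7 / 52.9 | 28.4 / 52.3 / 87.8% | 24.9 / 48.7 / 86.4% | 0.0100 / 0.0154 / 0.0478 |

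Table 1 implies 17.6 + 10.1 = 27.7% by look 2. The first row, which follows SAP 7.8, gives 39.9%, with a look-2 increment of 39.9 − 20.5 ≈ 19%.

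**5. Sensitivity to hazard shape (an assumption; the documents give none).** With Weibull shape 0.7, 0.5 and 0.3, the same six-month rates and completers only, success by look 2 is 35.5%, 32.6% and 29.9% with 16-month accrual, and 45.3%, 39.8% and 34.1% with 51-month accrual.

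**6. The look-2 boundary.** 2 × (1 − Φ(2.611)) = 0.0090, whereas p = 0.008 needs Z = 2.652; rounding does not bridge the two. Re-solving for cumulative alpha 0.015 at 14 and 19 events also gives Z = 2.611. A 32:50 information ratio gives 0.0079, so 0.008 fits spacing by patient counts, though the documents do not say how it arose. Look 1 (0.0100) and the final look (0.0405, shown as 0.04) agree with Table 2. At the planned completer looks, cumulative alpha 0.015 gives p = 0.0074 under either accrual period.

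**The case against.** The strongest reply is that no pass/fail decision rests on Table 1. Passing is set by the p-value limits, on which SAP Table 2 and protocol 12.8 agree; Z = 2.611 appears only in the software summary, and 0.008 is the stricter figure. The study is a feasibility trial meant to inform a pivotal design whether or not the test is significant. All of this stands and limits the consequence, but it does not make the row labels or the two boundaries agree.

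The size of the gap is also model-dependent. Counting only each subject's first six months would give 25.5% by look 2, below the stated 27.7%. Cut that way and ignoring dropout, 50 completers give 50 × 0.375 = 18.75 events, close to 19. But 32 completers then give 12 events, not 14, and SAP 7.10.2.4 uses all available follow-up. No calculation here models the 90-day blanking period, during which failures cannot count; the EaST model does not either. The caveat on size therefore stands, while the mislabelling holds under the printed design's own timings.

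The printout as reproduced has no upper-boundary crossing column under the alternative, so the link to Table 1 is a reconstruction. It matches all three increments and the total.

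**Conclusion.** Rows 1 and 2 of Table 1 are mislabelled: 17.6% and 10.1% belong to looks at 14 and 19 events among all accrued subjects. With constant hazards, 16-month accrual and the SAP 7.8 completer set, success by look 2 is about 40% analytically (about 38% simulated) instead of 27.7%, and the look-2 increment is about 19% instead of 10.1%. The figure falls to about 30% with a steeply falling hazard and rises to about 52% with 51-month accrual. Row 3's label is right; only its increment shifts. Separately, the SAP carries two look-2 limits, 0.0090 (derived from the printed Z) and 0.008.

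A reader might infer that type I error is lost. It is not: overall alpha with the Table 2 limits is 0.046 to 0.049 across the printed event counts and the readings tabulated above. A reader might also infer that the claim of at least 78% power is false. Analytic total power is about 79%; simulated values of 76 to 78% under 16-month accrual sit at or slightly below the claim, which is a matter of approximation and does not come from the mislabelling. Nor do the documents leave the operative look-2 rule open, since both tables state 0.008.

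**What to change.** At minimum, relabel Table 1 rows 1 and 2 as looks at 14 and 19 events among all accrued subjects, and state in SAP section 6 that 0.008, not Z = 2.611, is the operative look-2 limit.

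Preferably, re-run the design with looks at the events expected when 32 and 50 subjects reach six months, using the SAP 7.8 set and the accrual now expected; then restate the stage powers and replace the printout. That run alone will not reproduce 0.008: cumulative alpha of 0.015 gives about 0.0074 at look 2. So either change SAP Table 2 and protocol 12.8 to 0.0074, or keep 0.008 and restate the cumulative alpha at look 2 as about 0.0155 (overall about 0.048).

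The cost is one software run and small edits to SAP section 6, SAP Table 2 and, if the boundary or spend changes, protocol 12.8. No extra patients are needed and the look timing is unchanged.
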